Data collection: Yoga intervention and control participants (n=60) will complete baseline (March – May 2022), post-intervention (September – October 2022), and 3-month follow-up measures (January – February 2023) in-person at the University of Minnesota’s Epidemiology Clinical Research Center.

Post-intervention focus groups: Four groups (high attendance and low attendance from each intervention location) of randomly chosen intervention participants (anticipated n~20) will be invited to participate in a post-intervention focus group to assess intervention feasibility, acceptability, and safety with the overall program and specific components, and in order to inform program improvements. Focus groups will take place at the Epidemiology Clinical Research Center.

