## 5.0 Procedures Involved

### 5.1 Study Design:

Our proposed feasibility study will be two-arm, RCT with 60 participants randomly assigned to either an intervention group (n=30) or control group (n=30).

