### 5.2 Study Procedures:

Formative assessment focus groups will be conducted in April - June 2021. Data collected from these focus groups will be qualitative feedback on the proposed intervention strategies. The focus group guide is submitted with this IRB application.

Data collected directly related to the pilot RCT yoga intervention will be:

- Quality control data to make sure the yoga movements follow protocol and are safe for participants will be collected during the implementation of the yoga intervention. One yoga session will be randomly selected biweekly (during weeks 2, 4, 6, 8, 10, and 12) and videotaped so the content can be analyzed based on the established criteria related to poses, breathing and meditation. During these videotaped quality control sessions, participants will be asked to wear the activPAL to assess activity intensity.
- Acceptability of yoga classes will be assessed during the yoga intervention via a short self-reported survey after each yoga session. The survey is included with this application.
- Three, in-person data collection time points: baseline (March – May 2022), post-intervention (September – October 2022), and 3-month follow-up measures (January – February 2023). Data to be collected during these time points are:
  - Sedentary behavior will be assessed with the activPAL3 micro accelerometer (PAL Technologies, Glasgow, United Kingdom) for seven consecutive days at

- baseline before the start of the intervention, during three randomly selected weeks over the course of the 3-month intervention, and for one week at both the post-intervention and 3-month follow-up periods. The activPAL provides a valid and reliable measure of posture (sitting/lying vs. standing) for free-living settings and uses a transducer suitable for detecting lower intensity movements. The activPAL will be waterproofed using medical grade adhesive covering and attached to the midline of the thigh using a breathable, hypoallergenic tape. This method allows for the monitor to be worn continuously without removing for bathing or other water-based activities (a valuable feature that reduces missing data).

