- Blood pressure will be objectively measured using BpTRU BPM-200 (VSM MedTech Ltd, Coquitlam, Canada), an automated blood pressure recorder that has been validated against the mercury sphygmomanometer. Two blood pressures will be collected and averaged at each data collection time point following a five minute period of rest.
  - Stress will be measured in two different ways: biomarkers of physiological stress using cortisol saliva and perceived stress using questionnaires. Acute stress will be assessed using salivary cortisol levels taken at three different times (upon waking, 30 minutes after waking, and before going to bed) for 2 days at each data collection time point (assayed by UMN ARDL). Participants will be provided detailed instructions. Kits will be sent home with participants with clear instructions for capturing saliva samples in the morning and evening, and storing the date- and time-labeled plastic vials in their home freezer to be carried with them to their next clinic visit. Chronic stress will be assessed using common, valid self-report measures.
  - Additional measures: Trained research staff will collect height, weight, and body fat % using a Shorr Height measuring board and Tanita BF-350 scale, respectively, to calculate BMI. Diet will be assessed using NCI's web-based dietary recall, ASA-24, which has been validated in adults. A self-reported survey will be completed that inquiries on demographic characteristics (age, sex, marital status, education level, income), physical activity-related psychosocial variables (social support, self-efficacy, barriers, enjoyment), eating-related behaviors (intuitive eating, eating as a coping mechanism^72), and additional variables (collectivism, social connectedness, sense of belonging, community cohesion and embodiment). The survey with the listed measures is included with this application.

Post-intervention focus groups to assess intervention feasibility, acceptability, and safety with the overall program and specific components, and in order to inform program improvements will be completed September 2022. The focus group guide is submitted with this IRB application.

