## **11.0 Number of Participants**

### **11.1 Number of Participants to be Consented:**

For formative assessment focus groups, a maximum number of 16 (minimum of 12) participants will be enrolled for an average of 6-8 participants for each of the two focus groups.

For the pilot RCT, a maximum number of 60 (minimum of 54) participants will be enrolled for an average of 27-30 participants for each of the intervention and control groups. Participants enrolled in the intervention condition will be consented to participate in the yoga intervention eligible and the post-intervention focus groups.

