## **22.0 Consent Process**

### 22.1 Consent Process (when consent will be obtained):

This study will have two separate consent processes. Participants engaged in the formative assessment focus groups will be consented to complete those focus groups only. Participants enrolled in the pilot RCT will be consented to: a) participate in the study and to be randomized to either the intervention or control condition, and b) participate in the post-intervention focus groups, if allocated to the intervention group. After a participant is screened and identified as having met the eligibility criteria, participants will be asked to “consent and sign” the informed consent form. This will take place virtually for the formative assessment focus groups and in-person for the pilot RCT.

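### Yoga-arm focus groups end in September but post-intervention measurement runs through October with no stated order, so up to about two-thirds of the yoga arm could be measured after a programme discussion that controls do not have

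*Combined protocol and SAP*

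**What the plan says.** Section 5.2 gives the post-intervention measurement window as "post-intervention (September – October 2022), and 3-month follow-up measures (January – February 2023". Measures at each time point include seven days of activPAL wear, two days of home saliva sampling, blood pressure, and a survey covering, among other things, enjoyment, self-efficacy, social connectedness and sense of belonging. Perceived stress is also taken by questionnaire.

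The same section closes by saying that the focus groups, held "in order to inform program improvements will be completed September 2022". Section 4.1 describes them as "Four groups (high attendance and low attendance from each intervention location) of randomly chosen intervention participants (anticipated n~20". Their topics are feasibility, acceptability and safety of the programme. Section 22.1 limits attendance: women consent to "participate in the post-intervention focus groups, if allocated to the intervention group". Section 11.1 agrees. Section 8.1, read literally, has all 60 trial participants in these groups and should be reconciled with the other sections.

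Section 17.1 gives the groups a second task: where benchmark goals are missed, the reasons are to be explored there. One benchmark in Section 3.1 is that at least 90% of both arms complete the baseline, post-intervention and 3-month assessments.

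No section states the order of a woman's post-intervention measures and her focus group.

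**The concern.** The focus group is a research procedure, not part of the yoga programme, and only one arm receives it. A woman who has just spent a session with other programme members reviewing how it went may answer questions on stress, connectedness, belonging or enjoyment differently from one who has not. The assessment-burden rating would be open to the same influence if it is taken at that visit; the protocol does not say when it is taken. An effect on sitting time or cortisol is less plausible.

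Section 17.1 uses the outcome data to suggest effect sizes for a future trial and reports 95% confidence intervals. If some yoga women are measured after their group, those figures mix the programme with a discussion that a later programme would not necessarily include. Without recorded dates, the two could not be separated afterwards.

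The timing also works against the task set in Section 17.1. Completion of the post-intervention assessments is not known until measurement closes at the end of October, so groups that finish in September cannot discuss a shortfall in it.

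**Working it through.** **Inputs**
- Yoga arm: 30. Section 5.1 has "60 participants randomly assigned to either an intervention group (n=30) or control group (n=30". At minimum enrolment it is 27, since Section 11.1 has "a maximum number of 60 (minimum of 54) participants will be enrolled for an average of 27-30 participants for each".
- Focus-group members: about 20, all from the yoga arm (Sections 4.1 and 22.1).
- Focus groups: completed in September 2022 (Section 5.2).
- Measurement window: September and October 2022 (Sections 4.1 and 5.2). Taken as whole months, 30 + 31 = 61 days.

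**The plan's own figure.** The protocol gives no share of women exposed, so there is none to reproduce. The arm size checks: 60/2 = 30.

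**Step 1: ceiling.** If every member attends her group before being measured, the share is members divided by arm size:
- 20/30 = 66.7%
- 20/27 = 74.1% at minimum enrolment

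**Step 2: expected share for a given focus-group date.** Assume that visits are spread evenly over the 61 days, that visit dates are unrelated to focus-group attendance, and that all four groups meet on the same date. None of this is in the protocol. Then

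women exposed = 20 × (days left in the window after the group / 61), and share = women exposed / arm size.

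| Group date | Days left | Fraction of visits | Women (of 20) | Share of 30 | Share of 27 |
|---|---|---|---|---|---|
| 1 Sept | 60 | 60/61 = 98.4% | 19.7 | 65.6% | 72.9% |
| 15 Sept | 46 | 46/61 = 75.4% | 15.1 | 50.3% | 55.9% |
| 30 Sept | 31 | 31/61 = 50.8% | 10.2 | 33.9% | 37.6% |

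**Step 3: the wear week.** If the 7-day wear starts at the visit (assumed), a woman whose visit falls in the week up to her group has the group inside her wear period. The share with at least part of the wear exposed is then (46 + 7)/61 × 20/30 = 58% for 15 September and (31 + 7)/61 × 20/30 = 42% for 30 September.

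**Step 4: with measurement first.** If each member's measures are finished before her group, the exposed share is 0%.

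These steps count women exposed. They do not give the size or direction of any shift, and the documents contain nothing from which to estimate it.

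**The case against.** The strongest reply is that group discussion is already part of the treatment. Each 60-minute session ends with a sharing circle in which women give feedback together: three a week for 12 weeks, so up to 3 × 12 = 36. There are also six workshops and a private Facebook group. Beside that, one more discussion is a small increment. This stands as a limit on the likely effect. It does not remove the point: the circles belong to the programme whose effect is of interest, whereas the focus group is an evaluation procedure held after the programme has ended.

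Second, the design limits the damage. Aim 4 rules out comparisons between arms, Section 17.1 disclaims efficacy, and the attendance, fidelity and materials benchmarks are settled during the intervention. This also stands. A reader might infer that the overlap biases a treatment comparison or undermines the feasibility results; the documents support neither. What remains is the self-reported input to effect size expectations and, depending on when it is taken, the burden rating.

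Third, the protocol gives months, not an order, and staff could measure everyone first. A reader might infer that the plan intends focus groups before measurement. It does not say so; it only fails to prevent it. Sending missed benchmarks to the groups even suggests that results were expected first, but it sets no rule for an individual woman.

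Finally, a strict measurement-first rule could shut out women who skip assessments. Two of the four groups are for low attenders, whose views on retention are especially needed. The remedy has to allow for this.

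**Conclusion.** The point holds as a gap in scheduling with modest consequences. As written, the plan lets a yoga-only research procedure come before outcome measurement for up to about two-thirds of that arm (67%, or 74% at 27 women). A reader might take half as the maximum. It is not: about 50% is the expected share for mid-September groups under the even-visit assumption, and 34% is the figure for end-September groups.

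The ceiling rests on the protocol's anticipated 20 members, all attending. The expected shares also rest on the assumptions in Step 2. Exposure is possible rather than planned, and the effect is probably small and mainly on self-reported measures. The change is worth making because it is cheap, it keeps an avoidable one-arm influence out of data meant for the next trial, and it lets the groups address post-intervention assessment completion. It does not affect the 3-month follow-up, which comes after the focus groups in either case.

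**What to change.** In Sections 4.1 and 5.2:

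- Schedule focus-group invitees early in the measurement window, and hold each woman's group after her post-intervention visit, 7-day wear, saliva collection and survey.
- Let groups run past September where needed. The protocol schedules no measurement between the end of October and the January follow-up. To explore post-intervention assessment completion, at least some groups should meet after measurement closes.
- Keep women who miss or decline assessments eligible once their measurement slot has passed, so that low attenders are not lost.
- Record both dates for each woman, so that any departure from the order can be seen in the analysis.
- State when the burden rating is taken, and reconcile Section 8.1 with Sections 4.1, 11.1 and 22.1 on who attends.

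Sections 17.2 and 19.1 keep the measurement team blinded. Staff who already know the allocation should therefore hold the invitee list and focus-group dates, and some controls should be booked early too, so that an early slot does not reveal the arm.

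The cost is scheduling effort and slightly longer recall for some focus-group members. No added visits or measures are needed.

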### 5.3 Follow-Up:

The data to be collected at follow-up are outlined in the previous section: sedentary behavior using activPAL, blood pressure using an automated blood pressure recorder, stress using

salivary cortisol samples and a survey, height, weight, and body fat % measured by trained research staff, and a survey of additional measures.

5.4 Individually Identifiable Health Information:

PHI will not be collected from any participants.

**6.0 Data Banking**

N/A

**7.0 Sharing of Results with Participants**

7.1

Formative assessment and post-intervention focus groups: After each set of focus groups, research staff will summarize the findings in a report that will be shared with respective focus group participants. This methodology is referred to as member checking and allows the focus group participants the opportunity to provide feedback on whether the content of the summary accurately depicts what they wanted to share with the research staff.

Pilot RCT results: Findings from the pilot RCT will be shared with the participants through a presentation. Participants will have the opportunity to provide additional feedback and the research team will discuss plans for next steps. Additionally, the research team will utilize other online and media platforms, such as social media, infographics, videos, and podcasts, to disseminate our findings to a broader audience.

**8.0 Study Duration**

8.1

The duration anticipated for an individual participant's participation in the study is:

- Three months (April – June 2021) for 16 participants engaged in the formative assessment focus groups
- One year (March 2022 – February 2023) for the 60 participants enrolled in the pilot RCT who will also participate in the post-intervention focus groups

The duration anticipated to enroll all study participants is:

- Two months (April – May 2021) for the 16 participants engaged in the formative assessment focus groups
- Four months (February – May 2022) for the 60 participants enrolled in the pilot RCT who will also participate in the post-intervention focus groups

The duration anticipated to complete all study procedures and data analysis:

- Three years (November 2020 – October 2023)

**9.0 Study Population**

9.1 Inclusion Criteria:

- Self-identified as an African-American woman at least 18 years old;
- Engaging in less than 30 minutes/week of moderate-to-vigorous physical activity;
- If employed, working in a sedentary occupation that requires primarily seated work;
- If unemployed, typical day involves sedentary, primarily seated activities;
- Able to exercise for 20 minutes continuously;
- No pre-existing condition that limits physical activity;
- Have access to a computer (or mobile device) and internet service; and
- Vaccinated against COVID-19 *or* willing to provide proof of a negative test to attend any in-person components.

#### 9.2 Exclusion Criteria:

- Diagnosed with heart disease, diabetes, cancer, kidney, liver disease, major depression or bipolar disease;
- Take more than two daily medications for lipids or blood pressure; and
- Current smoker.

#### 9.3 Screening:

Participants will be initially screened via phone call for all participants (formative assessment focus group and pilot RCT participants). For pilot RCT participants only, eligibility will be verified during baseline data collection, which will take place at University of Minnesota's Epidemiology Clinical Research Center. Verification is not occurring for the formative assessment focus group participants because their involvement is 100% virtual and not in-person.

## 10.0 Vulnerable Populations

#### 10.1 Vulnerable Populations:

Population / Group	Identify whether any of the following populations will be targeted, included (not necessarily targeted) or excluded from participation in the study.
Children	Excluded from Participation
Pregnant women/fetuses/neonates	Included/Allowed to Participate
Prisoners	Excluded from Participation
Adults lacking capacity to consent and/or adults with diminished capacity to consent, including, but not limited to, those with acute	Excluded from Participation

medical conditions, psychiatric disorders, neurologic disorders, developmental disorders, and behavioral disorders	
Non-English speakers	Excluded from Participation
Those unable to read (illiterate)	Excluded from Participation
Employees of the researcher	Excluded from Participation
Students of the researcher	Excluded from Participation
Undervalued or disenfranchised social group	Targeted Population
Active members of the military (service members), DoD personnel (including civilian employees)	Excluded from Participation
Individual or group that is approached for participation in research during a stressful situation such as emergency room setting, childbirth (labor), etc.	Excluded from Participation
Individual or group that is disadvantaged in the distribution of social goods and services such as income, housing, or healthcare.	Excluded from Participation
Individual or group with a serious health condition for which there are no satisfactory standard treatments.	Excluded from Participation
Individual or group with a fear of negative consequences for not participating in the research (e.g. institutionalization, deportation, disclosure of stigmatizing behavior).	Excluded from Participation

Any other circumstance/dynamic that could increase vulnerability to coercion or exploitation that might influence consent to research or decision to continue in research.	Excluded from Participation
--	-----------------------------

### 10.2 Additional Safeguards:

By nature of the study, all participants will be minority women, specifically African-American women over the age of 18 years. African-American women are disproportionately affected with a sedentary lifestyle, excessive weight, hypertension, and stress. Over 60% of African-American women report being sedentary, and 80% are more likely to be at higher weight status ( $BMI > 25 \text{ kg/m}^2$ ) compared to non-Hispanic white women. These statistics underscore that a significant public health problem, a sedentary lifestyle, coupled with overweight/obesity, is associated with chronic diseases (e.g., hypertension) and psychological disorders. Decreasing sedentary behavior has mental, social, and psychological health benefits in adults, independent of total physical activity. Given the current state of health statistics in African-American women, finding innovative ways to decrease sedentary time in this population are of particular interest. Inclusion of African-American women is essential to the success of this project.

Pregnancy is an exclusion criterion at recruitment and during the intervention due to the possible risk of engaging in yoga if a participant is randomized to the yoga intervention group. However, if a participant becomes pregnant after the intervention has ended which overlaps with the post-intervention and follow-up data collection periods, they will be retained and included in the study. Data collection at all time points include completing an electronic survey, wearing an activity monitor that tracks physical activity with the request for participants not to alter their usual behavior, and collecting salivary samples which entails collecting less than an ounce of saliva over two days. All of the data collection are of minimal risk to pregnant women.

The potential adverse events anticipated in our pilot RCT would be injuries due to participation in yoga (e.g., muscle strain, fainting, falling) as well as other complications from comorbidities such as obesity, hypertension, diabetes and medication use. Participants will be instructed to call their healthcare provider and notify the research staff if they experience an injury or any adverse event. As a proactive measure, a detailed plan for monitoring risks, tracking and reporting adverse events will be established at the start of the study. Adverse events will be classified as severe (cause major disruption to participant's life, e.g. sprain, broken bone, cardiovascular event, death), moderate (causes minor inconvenience to participant, e.g. fainting spell, sore muscles for >3 days), and mild (no major impact on participant, e.g. headache, sore muscles for 2-3 days). The PIs will implement the data collection form for monitoring side effects and adverse events on a routine basis. The research assistants will administer this questionnaire weekly during the study to track any side effects or adverse events.

A Data Safety and Monitoring Board (DSMB) has been mandated by the funding agency, NIH. Members of the DSMC will be three senior PhD-level researchers including a biostatistician. The research staff will submit a written monitoring report to the DSMB twice a year (April and October).

To further protect participants, participants will clearly know that they can end participation at any time, researchers will provide information to participants for UMN IRB advisors to report any activity that the find troublesome, and research staff will undergo cultural sensitivity training.

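### Section 10.2 makes pregnancy an exclusion criterion, but the lists in 9.1 and 9.2 omit it, and 13.1 conflicts with applying it to a pregnancy that begins after screening

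*Combined protocol and SAP*

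**What the plan says.** Section 10.2 (Additional Safeguards) states: "Pregnancy is an exclusion criterion at recruitment and during the intervention due to the possible risk of engaging in yoga". The reason it gives is tied to one arm: "due to the possible risk of engaging in yoga if a participant is randomized to the yoga intervention group". The next sentence treats later pregnancies differently: "if a participant becomes pregnant after the intervention has ended", she is kept in the study. On the measurements, the same section says: "All of the data collection are of minimal risk to pregnant women".

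The eligibility lists are in 9.1 and 9.2. Section 9.1 has 8 bullets, and the nearest to pregnancy is "No pre-existing condition that limits physical activity". Section 9.2 has 3: a list of diagnoses ("Diagnosed with heart disease, diabetes, cancer, kidney, liver disease, major depression or bipolar disease"), a limit on daily lipid or blood pressure medications, and current smoking. Section 9.3 screens by phone and, for the pilot RCT, adds that "eligibility will be verified during baseline data collection". Table 10.1 marks the row for pregnant women, fetuses and neonates "Included/Allowed to Participate".

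On leaving the study, 13.1 says that the team will not withdraw anyone, gives rigorous screening as the reason, and leaves participants free to withdraw themselves. Section 13.2 says that no further data are sought from a participant who has withdrawn. Section 13.3 regards termination by staff as very improbable and allows use of data already in hand. Section 14.2 (Reproduction Risks) is marked as not applicable.

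**The concern.** An exclusion justified by a possible risk to the participant should appear where eligibility is defined. Here it appears only in a later section on vulnerable populations. Someone who takes 9.1 and 9.2 as the complete criteria would not find it.

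The second difficulty concerns the part of the exclusion that applies during the intervention. Screening cannot enforce that part, because the event may come afterwards. It needs a rule for women already randomised, and the only general rule on removal by the team, in 13.1, points the other way. Staff would have to choose between two sections in a matter that the protocol itself treats as one of risk.

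There is also a consequence for the data. Whether such a woman counts as withdrawn, or as a participant who has stopped yoga, determines whether her post-intervention and 3-month assessments are collected. It also affects how she enters the feasibility benchmarks in 3.1.

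**Working it through.** The plan has no figure to reproduce here. The check is a comparison of sections.

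**Step 1: the lists against the criterion.** Pregnancy is named in 0 of 8 inclusion bullets (9.1) and 0 of 3 exclusion bullets (9.2). The 9.1 bullet on pre-existing conditions is general and does not mention pregnancy, so it cannot stand in for a criterion that 10.2 states outright. The lists are incomplete against 10.2.

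**Step 2: each time of onset.**

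| Pregnancy | Section 10.2 | Other sections |
|---|---|---|
| Present at recruitment | Excluded | Not in 9.1 or 9.2 |
| Begins after screening, before the 12 weeks end | Excluded during the intervention; the contrast with the next row implies that she is not retained | 13.1: nobody is withdrawn by the team |
| Begins after the intervention | Retained | No conflict |

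The middle row can occur. Section 4.1 places baseline in March to May 2022 and the yoga sessions in June to August 2022, so eligibility is checked before the exclusion period has run. The reason given in 13.1 is screening, and screening cannot detect a pregnancy that begins later.

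**Step 3: what the middle row leaves open.**
- *Stop yoga or leave the study.* No section says which.
- *Arm.* The rationale in 10.2 concerns women randomised to yoga, but the exclusion is not worded by arm. Its application to controls during those 12 weeks is unclear.
- *Assessments.* If she counts as withdrawn, 13.2 ends data collection. If she only stops yoga, 13.2 does not apply and 10.2's view of the measurements would allow them to continue. The two readings give different datasets.

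**Step 4: weight of one case.** Section 3.1 sets benchmarks of at least 80% of intervention participants attending at least 80% of sessions, and at least 90% of all RCT participants completing the three assessments. At full enrolment one woman is 1/30 = 3.3 percentage points of the intervention arm and 1/60 = 1.7 points of all randomised participants. At the minimum in 11.1 these are 1/27 = 3.7 and 1/54 = 1.9 points. This is the weight of a single case if she stays in the denominator. It is not an expected number of cases.

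**The case against.** The best defence is that 10.2 already states the rule. It calls pregnancy an exclusion criterion in plain terms, so it is a criterion of this protocol wherever it is printed. Sections 9.3 and 22.1 refer to eligibility without limiting it to 9.1 and 9.2, screening staff are trained by the PIs (12.3), and the screening script, which is not in the documents, may well ask about pregnancy. This stands to the extent that wrongful enrolment is not shown. A reader might infer that staff would enrol pregnant women; the documents show only that the lists are incomplete.

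A reader might also take table 10.1 as a flat contradiction of 10.2. The documents do not support that. The form asks for one classification for the whole study, no row carries a timing limit, and 10.2 keeps women who become pregnant after the intervention, which largely explains the entry. A cross-reference is enough.

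Nor is it right that the plan is silent on pregnancy during the 12 weeks. Section 10.2 implies non-retention. What is missing is the procedure, together with agreement with 13.1.

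Finally, a reader might infer that pregnancies would go undetected, because the weekly adverse-event questionnaire is not described as asking about them and 4.1 plans no contact with controls during the intervention. The questionnaire's items are not reproduced, so that would be an argument from silence. The stated risk is that of yoga, which controls do not receive in that period.

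None of this removes the omission from 9.1 and 9.2 or the conflict between 10.2 and 13.1. No screening script, whatever it contains, can settle a pregnancy that begins after screening.

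**Conclusion.** The point holds as two inconsistencies. The eligibility lists omit a criterion that 10.2 states on grounds of risk. For a pregnancy beginning after screening and before the end of the 12 weeks, 10.2 and 13.1 conflict, and the action, the arm and the continuation of assessments are unstated.

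It should be fixed, and wording alone will do it. The documents give no pregnancy rate, so no number of affected women is claimed and no harm is asserted; 21.1 describes the research as no more than minimal risk. No effect on an efficacy comparison is claimed either, since 17.1 disclaims evaluation of efficacy. The conclusion rests on the protocol text alone and assumes nothing about the content of the screening script or the questionnaire.

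**What to change.** Reconcile 9.1/9.2, 10.2 and 13.1 to 13.3 so that all state one rule for recruitment and for the intervention period. The text should say:

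- which arm or arms the rule covers;
- whether a pregnancy that begins after screening means stopping yoga only or leaving the study;
- whether assessments continue, and so whether 13.2 applies.

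Carry the rule into the phone screen and the baseline eligibility check. Add a cross-reference from the pregnancy row of table 10.1 to 10.2, and check that the entry in 14.2 agrees with the risk named in 10.2. What the rule should be is for the investigators and the IRB.

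The cost is a wording amendment and a check of the existing screening script. It needs no extra participants or visits.
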